7.5.4 Methodology

The primary objective of this study is to evaluate the safety of two dose levels of PZ-128 compared to placebo as measured by the incidence of TIMI major plus minor bleeding not related to CABG through 30 days after treatment. Specifically, the study will be designed to test the hypothesis that from a safety perspective, PZ-128 is non-inferior to placebo, where non-inferiority is demonstrating that the difference in risk of bleeding incidence between the two treatments is less than a specified clinically important margin; the acceptable safety margin will depend in part on the efficacy benefit found for PZ-128. Specifically, the analysis of the bleeding outcome variables will assess the risks of bleeding on the two treatment regimens by generating point and one-sided 95% confidence interval estimates of the risk difference using the following formula:

$$\text{Risk Difference} = \pi_{\text{PZ-128}} - \pi_{\text{Pbo}}$$

where $\pi_{\text{PZ-128}}$ is the bleeding incidence across the two PZ-128 arms and π_{Pbo} is the bleeding incidence for the placebo arm. The point and interval estimates for this risk difference will be obtained using a generalized linear model with the binomial distribution assumption and an identity link. To address the potential underlying risk differences associated subpopulations defined by underlying subject risk and whether or not the subject received CABG, those factors will be included in the model. The robust variance estimator as defined by Liang and Zeger [49] will be used to generate the interval estimates. Comparable models will be used to generate estimates for both the primary outcome and the secondary outcomes defined above.

Adverse Events

National Cancer Institute Common Terminology Criteria for Adverse Events (NCI CTCAE) version 4.0 will be used for AE/SAE reporting in the trial database. This version of CTCAE is MedDRA v12.0 (Medical Dictionary for Regulatory Activities Terminology) compatible at the AE (Adverse Event) term level where each CTCAE term is a MedDRA LLT (Lowest Level Term). All adverse events will be captured from the time of randomization up until 30 days after study drug administration and all serious adverse events will be captured from the time of randomization up until 90 days after study drug administration. AEs will be summarized by system organ class and preferred term using MedDRA, with summaries reported separately for the 3 treatment arms aggregated across all participants in those treatment arms, and stratified by the four risk groups defined by the cross-classification of whether subjects received CABG or not and the urgency of the procedure at the time the operator decides to perform the cardiac catheterization (i.e., elective versus urgent). All adverse event data will be listed for all subjects. Separate listings of all SAEs, deaths and discontinuations due to AEs will be presented. Adverse event data will be summarized by relationship and severity. All AEs relating to bleeding will be summarized separately.

Laboratory data

All laboratory data will be listed and absolute values outside the normal range will be flagged if applicable. Changes from pre-dose baseline at Screening may also be summarized. Numerical laboratory data will be summarized using standard summary statistics and will be presented by treatment group.

Other safety data

Physical examination, ECG, and vital signs data will be listed and summarized using standard summary statistics by treatment group.

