Clinical evaluations including physical examinations, vital signs, laboratory tests, electrocardiograms and the assessment of adverse events will be performed for all subjects during hospitalization and at follow-up time points as measures of the safety profile.

Randomization: Randomization will be conducted prior to the diagnostic angiography.

Stratification: Randomized assignment of PZ-128 and placebo will be stratified for whether the cardiac catheterization ± PCI is being done on an elective or urgent basis at the time the operator decides to perform the procedure.

Sample Size/Power: The current design anticipates a sample size of 600 subjects who will undergo non-emergent cardiac catheterization ± PCI. The sponsor anticipates that the incidence of major plus minor bleeding among placebo-treated subjects will range from 2% to 6% on the basis of historical experience. Given the anticipated sample sizes and estimated range of incidences associated with placebo, the study will be able to demonstrate that the bleeding risk of PZ-128 is non-inferior to the risk associated with placebo with non-inferiority margins in the range of 2.6 to 7.6%, depending on the underlying bleeding risk of placebo. Given the anticipated benefits of PZ-128, these non-inferiority margins are reasonable for the planned safety decisions generated from this trial.

Statistical Methods: All subjects who are randomized will be considered evaluable for the analyses. The following statistical analysis will be provided for the primary endpoint. The point estimate of the difference in risk of any event of non-CABG TIMI major plus minor bleeding through 30 days post treatment for between PZ-128 and placebo (e.g., Pr (Event in PZ-128 patient)-Pr (Event in placebo patient)), and corresponding lower one-sided 95% confidence interval will be presented. These estimates will be generated using subjects who underwent diagnostic angiography for all PZ-128 treatment arms pooled across both doses (~400 subjects) and all placebo (~200 subjects) and descriptive results will also be generated for each individual dose. The proposed phase 2 study is not of sufficient size or of sufficient follow-up duration to allow formal analysis of clinical efficacy.

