Approved by the U.S. Food and Drug Administration (FDA) in 2014 for secondary prevention of cardiac events, the PAR1 antagonist, vorapaxar (SCH 530348) is marketed by Merck & Co, Inc. (Whitehouse Station, NJ) and E-5555 (atopaxar) was developed by Eisai Company, Ltd. (Japan). Vorapaxar, an orally active, synthetic analog of himbacine with high affinity ($K_i = 3\text{-}8\text{ nM}$) [25] to PAR1, has an exceptionally long elimination half-life of 6.6-13 days [26] and a functionally irreversible binding mode [27]. The pharmacodynamic half-life typically exceeds the entire lifespan of a circulating platelet with 50% recovery of platelet function by 4-8 weeks after a single 20 or 40 mg loading dose of vorapaxar [28]. The onset of inhibition of vorapaxar on PAR1 activity occurs by 2 h after receiving the loading dose. A phase 2 randomized clinical trial, TRA-PCI, tested the safety, tolerability and preliminary efficacy of this compound in 1030 subjects undergoing non-emergent cardiac catheterization with intent to perform percutaneous revascularization [29]. The trial was designed as a sequential randomization scheme. First, prior to angiography all subjects were randomized 3:1 to receive one of three loading doses (10, 20 or 40 mg) or matching placebo. Subsequently, only those who actually underwent PCI ($n = 573$; 56% of the total cohort) – representing the primary cohort of interest – were further randomized to a 60-day maintenance treatment of 0.5, 1 or 2.5 mg or matching placebo. The PCI cohort also received unfractionated heparin, low-molecular-weight heparin, or bivalirudin, and a loading dose of clopidogrel (300-600 mg) and aspirin (162-325 mg oral or iv 150-500 mg). The incidence of the primary endpoint of TIMI major plus minor bleeding was low overall (3% in both the treatment and placebo groups) and no significant differences were observed in the primary cohort between the placebo and study drug groups. Similarly, TIMI major plus minor bleedings were not significantly different in both of the secondary cohorts of subjects medically managed and surgically revascularized. Although the study was not powered to detect these differences, the composite endpoint of death, major cardiac adverse event or stroke was proportionately less in subjects treated with any vorapaxar dose ($n = 24$; 6%) than with placebo ($n = 13$; 9%; odds ratio 0.67; 95% CI 0.33, 1.34), a difference mainly driven by a reduction of the myocardial infarction (MI) component in vorapaxar-treated subjects. Also, a dose-effect relationship was observed, with the 40 mg loading dose achieving the strongest reduction in the rate of MI. This study suggested a potential benefit with trends towards lower thrombotic events, without an increased bleeding risk and encouraged the development of phase 3 trials to evaluate the clinical benefit of vorapaxar in combination with current standard-of-care dual antiplatelet therapy in high risk subjects with coronary artery disease.

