7.2 General Aspects of Statistical Evaluation

Statistical analyses will be performed using SAS version 9.23 and, where appropriate (e.g., specific pharmacokinetic analyses) other validated software. Statistical analyses will be performed in accordance with the study protocol, and a comprehensive Statistical Analysis Plan (SAP) which will be prepared before unmasking of the data. The SAP will provide further details of the analyses and presentation of the data and will contain ground rules and data handling conventions used to perform the analyses. Both the data and the proposed methods of analyses will be reviewed continuously during the study by the study team, which includes input from statistical, clinical and data management personnel. Before database lock, a masked review will take place during which all important protocol deviations will be discussed and agreed by the team and any ambiguities in study outcomes will be adjudicated in a masked fashion by the protocol team.

The primary and secondary outcome measures will be treated as binary outcomes with any individual experiencing the event within the specified time frame after treatment classified as

positive for the outcome and other individuals classified as negative. Details of the measures will be included in the SAP.

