7.6.2 Methodology

The proposed phase 2 study is not of sufficient size or of sufficient follow-up duration to allow analysis of clinical event rates.

Two alternative approaches will be used to evaluate the differences in risk of the various secondary outcome measures. The first will utilize generalized linear models analogous to those used for the safety outcomes. In addition because each of these outcome measures can be evaluated using a time to event approach, survival analyses will be used to examine those outcomes. Kaplan-Meier estimates of the cumulative risk of each outcome will be calculated to investigate differences between the treatment groups in the time to occurrence, and a Cox Proportional hazard model that accounts for the risk stratification variables described above will be used to assess risk differences in the 3 treatment groups. All of these analyses will be interpreted descriptively, with no adjustment for multiple comparisons. We anticipate that some analyses will be conducted for specific subgroups (e.g., influence of baseline risk factors, concomitant therapies), but these subgroup analyses will again be considered exploratory and treated as descriptive analyses. Details will be provided in the SAP. Generalized linear models comparable to those used for the safety outcomes will also be used to evaluate the effect of investigator choice of P2Y₁₂ inhibitor on each of the MACE components.

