7.7 Determination of Sample Size/Power

Power calculations were used to evaluate the size of non-inferiority margins that were able to be detected from a study of 600 participants, 400 of whom are randomized to PZ-128 and 200 of whom are randomized to placebo. Available data on bleeding rates from previous studies [29, 32, 33] suggest that the incidence of bleeding in the placebo arm is likely to be in the range of 2% to 6%. Furthermore, the sponsor assumes that the true difference in the incidence

of the participants on the PZ-128 arms and those in the placebo arms are likely to be in the range of 0% to 2%. Based on these assumptions, the table below shows the minimum non-inferiority margin that could be demonstrated with at least 80% power, where that non-inferiority margin is based on the upper limit of the 95% confidence interval identified above. This sample size is adequate to demonstrate acceptable upper safety bounds.

True Incidence or Risk of Bleeding for placebo	Minimum Demonstrable Non-inferiority margin	
	True Incidence Difference of 0%	True Incidence Difference of 2%
2%	2.6%	5.0%
3%	3.2%	5.5%
4%	3.7%	5.9 %
5%	4.1%	6.3%
6%	4.4%	6.6%

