7.8 Interim Analysis

Although no formal stopping boundaries will be utilized, one interim safety analysis will be performed at approximately 1 year following the enrollment of the first subject, or after enrollment of 50% of the study population, whichever occurs first. The Data and Safety Monitoring Board (DSMB) will be provided point and interval estimates of PZ-128 benefit at the time of that analysis based on survival estimates, and will evaluate evidence of bleeding risk in light of the potential efficacy benefits in making recommendations about stopping the trial.

An independent DSMB, as described in **Section 9.3.1**, will monitor safety data on an ongoing basis to ensure that subject safety is not compromised. The DSMB-supporting statistician will have access to the randomization code to allow grouping of the safety data. The DSMB will receive blinded data but has the option to unblind the data if deemed warranted. The DSMB will make safety recommendations for the alteration or termination of the study to the study sponsor.

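### The primary bleeding non-inferiority test has no chosen margin, and the plan lets the margin move with the efficacy observed in the same trial

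*Combined protocol and SAP*

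**What the plan says.** Section 7.5.4 states that "the study will be designed to test the hypothesis that from a safety perspective, PZ-128 is non-inferior to placebo". It defines this as a difference in bleeding risk below a clinically important margin. The margin is described as specified, but no number follows, there or elsewhere. The same sentence continues that "the acceptable safety margin will depend in part on the efficacy benefit found for PZ-128".

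Two places give numbers, and neither selects one:

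- Section 7.7 says that "Power calculations were used to evaluate the size of non-inferiority margins that were able to be detected from a study of 600 participants". Its table lists ten minimum demonstrable margins, 2.6% to 6.6%, for placebo risks of 2–6% and true differences of 0% or 2%.
- The Synopsis (Sample Size/Power) gives a range of 2.6 to 7.6% and concludes: "Given the anticipated benefits of PZ-128, these non-inferiority margins are reasonable for the planned safety decisions generated from this trial".

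On efficacy, Section 7.6.2 says the study "is not of sufficient size or of sufficient follow-up duration to allow analysis of clinical event rates" and that the efficacy analyses will be read descriptively, without multiplicity adjustment. Section 7.2 promises "a comprehensive Statistical Analysis Plan (SAP) which will be prepared before unmasking of the data". It does not say that document will fix a margin. Section 7.8 says the DSMB "will be provided point and interval estimates of PZ-128 benefit at the time of that analysis based on survival estimates".

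**The concern.** A non-inferiority test needs its threshold before the data are seen. Here the threshold is absent, and the one statement about how it will be set makes it depend on an outcome of the same trial. That outcome is one the plan calls too imprecise for formal analysis, so a chance difference in MACE could be used to justify a wider bleeding margin for the primary conclusion. The listed margins describe what 600 subjects can show. They do not say what excess of bleeding is clinically acceptable.

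The result feeds a real decision: Section 4.1.2.2 says the findings will inform whether to proceed to Phase 3 and with what regimen.

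**Working it through.** **1. The plan's own margins (Section 7.7).** With d the true difference, pT and pC the true risks, and 400 and 200 subjects:

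M = d + (z for the bound + 0.842) × sqrt[pT(1−pT)/400 + pC(1−pC)/200]

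At placebo 3% and d = 0 the root is sqrt(0.03 × 0.97 × 0.0075) = 1.477 points. A one-sided 95% bound gives 2.487 × 1.477 = 3.7%; the table says 3.2%. A one-sided 90% bound gives 2.124 × 1.477 = 3.14%, which rounds up to 3.2%. All ten cells match the 90% bound in this way and none matches 95%. The Synopsis maximum of 7.6% is not in the table. Both are separate points. Below, the table values serve only as the plan's own candidate margins.

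**2. How much the choice matters on identical data.** Non-inferiority is met if U < M, where

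U = observed difference + 1.645 × sqrt[p̂T(1−p̂T)/400 + p̂C(1−p̂C)/200].

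With 8/200 placebo bleeds (4.0%):

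- 15/400 on PZ-128: U = −0.25 + 1.645 × 1.680 = 2.5%. 16/400 gives 2.8%. So 15 is the most that passes at M = 2.6%.
- 33/400 on PZ-128: U = 4.25 + 1.645 × 1.953 = 7.5%. 34/400 gives 7.7%. So 33 is the most that passes at M = 7.6%.

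Any count from 16 to 33 is a failure or a success depending on where in the Synopsis range the margin falls.

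**3. Error with a margin fixed in advance.** Exact binomial enumeration, 400/200, unadjusted Wald bound, placebo 3%, true excess equal to the margin:

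| Fixed margin | 2.6% | 3.2% | 4.4% | 5.5% | 6.6% | 7.6% |
|---|---|---|---|---|---|---|
| P(declare) | 0.042 | 0.043 | 0.045 | 0.045 | 0.046 | 0.050 |

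Fixing any of these controls the error.

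**4. Error when the margin follows observed efficacy.** The plan gives no rule, so these are assumptions:

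- The margin moves between the two table values in a row.
- The true excess equals the narrower value, which is the null boundary for it.
- There is no true MACE effect, and MACE is independent of bleeding.
- MACE is 6–9% in both arms. The range comes from the earlier vorapaxar PCI trial in Section 4.1.1, where a similar composite "was proportionately less in subjects treated with any vorapaxar dose" (6% against 9% on placebo).

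With equal true MACE, the observed rate favours PZ-128 with probability 0.469 (MACE 6%) to 0.474 (MACE 9%). It does so by at least 2 points with probability 0.180 to 0.223.

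At placebo 3% and a true excess of 3.2 points, P(declare) is 0.0427 at M = 3.2% and 0.3791 at M = 5.5%. Mixing the two:

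- Any observed benefit, MACE 6%: 0.531 × 0.0427 + 0.469 × 0.3791 = 0.200 (0.202 at MACE 9%).
- Benefit of at least 2 points, MACE 6%: 0.820 × 0.0427 + 0.180 × 0.3791 = 0.103 (0.118 at MACE 9%).

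| Placebo risk | Margins | Fixed at narrower | Widened on any benefit | Widened on ≥2 points |
|---|---|---|---|---|
| 2% | 2.6% to 5.0% | 4.3% | 27% | 13–15% |
| 3% | 3.2% to 5.5% | 4.3% | 20% | 10–12% |
| 4% | 3.7% to 5.9% | 4.4% | 16–17% | 9–10% |
| 5% | 4.1% to 6.3% | 4.4% | 15% | 8–9% |
| 6% | 4.4% to 6.6% | 4.3% | 14% | 8–9% |

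Replacing independence by a latent bleeding–MACE correlation of 0.3 (20,000 simulated trials, placebo 3%) gives 21% and 11–13%.

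**The case against.** The best defence is that this is in practice an estimation study. Section 7.5.4 goes on to specify a point estimate and one-sided interval, and no section writes out a decision rule. The interval can be read against any margin. A statement that the excess is below a named M is wrong in about 5% of trials or fewer, even if M is named afterwards. That is correct, and it limits the point to the declaration. But the Synopsis, Section 4.2.1 and Section 7.5.4 all call this non-inferiority, and Section 7.5.4 calls it a hypothesis to be tested.

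Second, the later SAP could fix the matter. It could, but a single number fixed before unmasking would contradict Section 7.5.4, because efficacy by arm is known only afterwards. A written rule mapping benefit to margin would be consistent and its error rate could be computed. No such rule appears, and it would still rest the primary conclusion on an efficacy estimate the plan considers unfit for inference.

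Third, the switch rule is invented, the table values were not offered as alternative margins, and a 3.2-point excess lies outside the sponsor's 0–2% planning range. All true. The 14–27% shows what the clause permits; it is not the plan's error rate, and it is an error only against the narrower margin.

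Fourth, a clinically chosen margin may prove too tight for 600 subjects. With an assumed 4% margin and placebo risk 4%, exact power is 78% at no true difference and 28% at a true difference of 2 points. This stands, and bears on the cost of the fix.

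**Conclusion.** The concern holds. The primary hypothesis has no fixed success criterion, and the plan states that the criterion will depend partly on the efficacy found. This must be corrected, because a margin chosen after unblinding cannot be defended as prespecified.

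The text alone establishes the defect. Its size depends on the assumptions in the working. Against 4.3–4.4% with the narrower margin fixed, false declaration rises to 14–27% if any observed MACE benefit widens the margin, and to 8–15% if at least 2 points are required. The figures use an unadjusted Wald bound, whereas the plan's model also includes covariates. The coverage of the one-sided bound is not in question.

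**What to change.** 1. In Section 7.5.4, delete the clause that ties the margin to the efficacy found.
2. Record one absolute margin, with its clinical justification, in the protocol and SAP before any unblinded look, including the interim in Section 7.8. State that non-inferiority is concluded only if the upper one-sided 95% limit lies below it.
3. If the sponsor will not fix a margin, remove non-inferiority from the design description and hypothesis. Report the risk difference already specified, with its upper one-sided 95% limit, as estimation.
4. Keep the benefit–risk assessment of Section 7.6.1 as a separate descriptive step.

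**Cost.** The edits are to wording only; data collection and the specified model do not change. The sponsor gives up the freedom to choose the margin afterwards. Power against the chosen margin should be stated. If 600 subjects fall short and the sample size is to stay, step 3 is the honest route.

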After written informed consent is obtained, eligibility tests/evaluations will be performed. All screening assessments must be completed prior to randomization and be within 14 days of the study drug treatment (this may include standard of care preadmission testing for the planned procedure). For the purposes of this study, a subject is considered enrolled into the trial upon successful randomization and an assignment of study drug and a unique subject randomization number. On the day of the procedure, subjects will receive a dose of aspirin (81-325 mg) orally. Subjects will receive the randomized assignment of PZ-128 or matching placebo as a single, 2-hour continuous IV infusion, to be initiated within 1 hour prior to the start of the cardiac catheterization procedure (defined as the time of the arterial sheath placement prior to the diagnostic angiography) in a 2:2:1:1 parallel, double-blind fashion of either: **1) PZ-128 0.3 mg/kg, 2) PZ-128 0.5 mg/kg, or 3) Placebo 0.3 mg/kg, or 4) Placebo 0.5 mg/kg.**

If PCI is deemed necessary and appropriate during catheterization, an anticoagulant (unfractionated heparin or low-molecular-weight heparin) will be added and a loading dose of an oral P2Y₁₂ inhibitor (clopidogrel, prasugrel or ticagrelor) will be administered per investigator choice and standard of care guidelines before PCI. All other subsequent therapy or care provided and not specified by the protocol will be in accordance with the local standard.

PCI successfully begins when the guide wire crosses the lesion, regardless of any subsequent event or process, including completion of the intended procedure. The planned treatment with any GP IIb/IIIa Inhibitor (GPI) during the PCI will not be allowed, but investigators may use these agents as a thrombotic bailout if indicated. Following the procedure, subjects will be advised regarding continuing/maintenance treatment with aspirin and a P2Y₁₂ inhibitor according to local standard of care.

If a PCI is not indicated during catheterization, or is indicated but does not commence (guide wire does not cross the lesion) for any reason, the subject will undergo medical management or surgical revascularization (i.e., CABG) according to the local standard of care.

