6.7.1.3 Other Secondary Endpoints Related to Safety

Other secondary safety endpoints include the incidences of the following:

1. TIMI minimal bleeding not related to CABG (defined as clinically significant overt signs of bleeding associated with a drop in hemoglobin concentration of < 3 g/dL (or hematocrit of $< 9\%$) that does not otherwise meet criteria for major or minor bleeding) through 30 days after treatment;
2. “clinically significant” bleeding (defined as TIMI major or minor bleeding or bleeding requiring medical attention) through 30 days after treatment; and

3. TIMI bleeding related to CABG through 30 days after treatment (subjects who undergo CABG will specifically have assessment of (a) surgical wound bleeding using quantitative total chest tube drainage in the first 24 hours; (b) need for transfusion of blood products in the first 48 hours; and (c) need for surgical re-exploration).

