7.5.1 Primary Endpoint

The overall objective of this study is to evaluate the safety of two dose levels of PZ-128 compared to placebo. The outcome used to assess the safety of PZ-128 will be the incidence of major and minor bleeding events, as assessed by the TIMI system of classification, when PZ-128 or placebo is added to the standard of care (dual anti-platelet therapy with aspirin and P2Y₁₂ inhibitor) in subjects undergoing non-emergent PCI or non-emergent cardiac catheterization with the intent to perform PCI.

The primary safety outcome variable is the incidence of TIMI major plus minor bleeding not related to CABG through 30 days after treatment.

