7.5.2 Secondary Safety Endpoints

The secondary safety outcome variables will be the following:

- incidence of bleeding that does not meet the TIMI criteria for major or minor (i.e., minimal bleeding) through 30 days after treatment;
- incidence of “clinically significant” bleeding through 30 days after treatment (TIMI major or minor or bleeding requiring medical attention);
- incidence of TIMI bleeding related to CABG through 30 days after treatment;

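### The primary risk-difference model adjusts for receipt of CABG, which is decided after randomisation; the sparse CABG cell often pushes the identity-link fit onto the zero-risk boundary, and no fallback is named

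*Combined protocol and SAP*

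**What the plan says.** Section 7.5.4 says that the point and interval estimates of the risk difference are "obtained using a generalized linear model with the binomial distribution assumption and an identity link", with a robust variance. On covariates it says of "underlying subject risk and whether or not the subject received CABG, those factors will be included in the model". It then extends the method: "Comparable models will be used to generate estimates for both the primary outcome and the secondary outcomes defined above".

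The timing is clear. The Synopsis states: "Randomization will be conducted prior to the diagnostic angiography". Under Section 6.1, if PCI is not indicated or does not commence, "the subject will undergo medical management or surgical revascularization (i.e., CABG) according to the local standard of care".

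The primary endpoint in Section 7.5.1 is the "incidence of TIMI major plus minor bleeding not related to CABG through 30 days after treatment". The secondary safety endpoints in Section 7.5.2 include the "incidence of TIMI bleeding related to CABG through 30 days after treatment".

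Section 7.7 takes placebo bleeding of 2% to 6% and a true difference of 0 to 2 points, and bases the non-inferiority margin on the upper confidence limit. Section 7.2 leaves further analysis detail to a SAP to be written before unmasking. The supplied text has no rule for a model that fails to converge or fits a risk of zero.

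**The concern.** Receipt of CABG is known only after randomisation and after the infusion has begun. A comparative model should not condition on it. Because the primary endpoint leaves out CABG-related bleeding, the main practical trouble is fit rather than overlap with the outcome.

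An identity-link binomial model must keep every fitted risk at or above zero. A small group with few or no events pulls its fitted risk to that limit. The score equations then have no interior solution, and the robust variance loses its justification. The upper limit that carries the non-inferiority judgement then depends on how the software handles the failed fit.

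For CABG-related bleeding the literal reading is worse: subjects without CABG cannot have the event, so a model fitted to all subjects with a CABG term can never have an interior solution.

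**Working it through.** **The plan's own figures.** The plan gives no boundary or non-convergence rate to reproduce. Its nearest figure is the Section 7.7 margin of 2.6% (2% placebo bleeding, no true difference, 400 vs 200, 80% power). At one-sided 5%, (1.645 + 0.842) × √[0.02 × 0.98 × (1/200 + 1/400)] = 3.0%, so that entry does not reproduce. This is a separate matter and does not affect what follows.

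**Inputs from the documents.** 400:200 allocation; placebo bleeding 2%, 4%, 6%; true difference 0 or 2 points; identity link; robust variance; one-sided 95% limit.

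**Inputs assumed, because the documents give none.** CABG in 5-10% of subjects (30-60 of 600); CABG-to-non-CABG bleeding risk ratio r of 0.5, 1 or 2; underlying subject risk read as urgency (the factor crossed with CABG in the adverse-event part of Section 7.5.4), with 40% urgent at 1.4 times the risk.

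**Why the boundary is reached.** Write the risk as p = a + bT + uU + cC, with C = 1 for CABG. The score equation for c is Σ over CABG subjects of (y − p)/[p(1 − p)] = 0. If no CABG subject has a counted bleed, every y is 0 and the sum is −Σ 1/(1 − p), which cannot be zero. Zero events in the CABG cell therefore guarantee a boundary fit.

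A hand check with no true difference: for overall risk p and CABG share s, the CABG risk is q = rp/(1 − s + sr), and the chance of an empty cell is about (1 − q)^(600s).

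| p | s | r | q | Expected events | Chance of none |
|---|---|---|---|---|---|
| 2% | 5% | 0.5 | 1.03% | 0.31 | 73% |
| 2% | 5% | 2 | 3.81% | 1.14 | 31% |
| 2% | 10% | 2 | 3.64% | 2.18 | 11% |
| 6% | 5% | 0.5 | 3.08% | 0.92 | 39% |
| 6% | 5% | 2 | 11.43% | 3.43 | 3% |

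These are floors, since a cell with events can also end on the boundary.

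**Simulated boundary rates.** Constrained maximum likelihood, 36 scenarios × 2,000 trials; boundary means a minimum fitted risk below 0.00001.

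| Placebo bleeding | With CABG term | Ratio 2 only | Without CABG term |
|---|---|---|---|
| 2% | 36-79% | 36-50% | 19-21% |
| 4% | 9-62% | 9-19% | 2-3% |
| 6% | 2-54% | 2-6% | under 1% |

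Repeating this at 2% bleeding and no true difference on a wider grid (CABG 3-15%, risk ratio 0.5-4, urgent share 20-50%, urgent relative risk 1-2) gave 33-89% with the term and 13-33% without. The term raised the rate in every scenario, by at least about 16 points.

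**Coverage of the one-sided 95% upper limit.** With no true difference: 95-97% with or without the term. With a true 2-point excess:

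| Risk ratio | Constrained fit, with term | Ordinary GLM output, with term (5% CABG) |
|---|---|---|
| 0.5 | 79-83% | 88-92% |
| 1 | 87-92% | 93-95% |
| 2 | 91-95% | 94-95% |

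Without the term, coverage was 93-97%. In boundary trials the two routines gave upper limits more than 0.5 points apart in 36-63% of cases. The ordinary GLM was run in statsmodels; SAS, which the plan names, was not available.

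**False non-inferiority.** With the true excess set at 2.6, 3.7 or 4.4 points (5% CABG, nominal 5%): 5-8% for ordinary GLM output and 5-14% for the constrained fit with the term, 4-7% without.

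**Point estimate.** In boundary trials it sits a median 0.2-0.6 points from the raw difference. Large-sample bias is at most 0.09 points if the drug does not change CABG use.

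**CABG-related bleeding in all subjects.** The score equation for c makes the CABG sum zero. Subtracting it from the intercept equation leaves −Σ 1/(1 − p) = 0 over subjects without CABG, which is impossible at any event rate.

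**The case against.** The strongest reply is that the numbers show a sparse cell under an identity link, not harm from conditioning on a post-randomisation variable. A baseline covariate of 5-10% prevalence would behave the same way. That is right: the simulations let CABG use be independent of treatment, so they do not measure post-randomisation bias.

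Second, a boundary fit is not always a visible failure. An ordinary GLM routine usually returns an answer with a milder loss of coverage, and the worst figures come from a constrained fit the plan does not name. This also stands, but the gap between routines is itself the difficulty when no rule is stated.

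Third, the sizes depend on undocumented CABG shares and risks, and 2% is the bottom of the plan's range. At 6% the excess is small if CABG subjects bleed twice as often as others. The Section 7.7 margins are also not decision thresholds, since Section 7.5.4 ties the acceptable margin partly to efficacy, so the false non-inferiority rates are illustrative.

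Fourth, the promised SAP may contain a fallback. It may, but a SAP that follows Section 7.5.4 would carry the CABG term forward, because the text commits to it.

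Fifth, comparable models need not be identical ones. The Synopsis plans a CABG cohort, and Section 6.7.1.3 says "subjects who undergo CABG will specifically have assessment of" specific items, which points to an analysis within CABG subjects. Such a fit would avoid the impossibility, but Section 7.5.4 does not say that it is intended.

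**Conclusion.** The concern holds and should be fixed; confidence is medium because the sizes rest on assumed inputs. The plan commits to a post-randomisation covariate in the primary model and names no fallback. The excess of boundary fits is robust near 2% bleeding; at 6% it is large only if CABG subjects bleed no more than others. Upper-limit coverage suffers when there is a true 2-point excess, the top of the plan's own range, mainly when CABG subjects bleed no more than others.

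Two things limit the severity. There is no loss when the true difference is zero, and the Synopsis describes a risk difference without mentioning covariates, although it does not present this as a fallback. Part of the problem at 2% belongs to the identity link itself: about 20% of fits reach the boundary without CABG.

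**What to change.** 1. Delete receipt of CABG from the comparative models in Section 7.5.4. Adjust only for the randomisation factors in Section 6.4.4: urgency, and site where feasible.
2. Pre-specify a risk-difference estimator that always exists, with an upper one-sided 95% limit. One example is Mantel-Haenszel stratified by the randomisation factors. With the Sato variance and three sites × urgency (36 scenarios × 3,000 trials) it was computable every time, with coverage of 95.2-96.9%. Use it as the primary method, or as the stated fallback when the identity-link model does not converge or fits a risk at or outside 0-1. Removing CABG alone is not enough.
3. Report CABG-related bleeding as counts and percentages by arm among CABG subjects, without this model.
4. Keep the planned PCI, CABG and medical-management cohorts descriptive.
5. Optionally, state in Section 7.6.2 that the risk stratification variables are baseline variables; the present wording is only unclear.

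The cost is wording and programming before unblinding. No new data are needed.
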